17 EFFICACY ASSESSMENTS

Efficacy assessments will be evaluated at times specified in the Schedule of Study Events (Table 7-1) for composite indices including DAS28-ESR, ACR20/50/70, and CDAI; as well as FACIT-F and HAQ-DI.

The DAS28-ESR is a validated composite index to assess disease activity in RA (Prevo et al, 1995; DAS28 Website, 2016). The components of DAS28-ESR include 28 Joint Count, General Health VAS, and ESR.

The ACR has developed a core set of criteria for defining improvement in RA that includes 28 Joint Count, Patient Assessment of Pain, Patient Global Assessment of Disease Activity, Physician Global Assessment of Disease Activity, Patient's Assessment of Physical Function using the HAQ-DI, and an acute phase reactant (ESR or CRP). Typical thresholds for ACR improvement are 20%, 50% and 70% (ACR20, ACR50, ACR70), with the percentages referring to the improvement in tender and swollen joints plus improvement in 3 of the 5 other components (Felson et al, 1995; Felson and LaValley, 2014; Pincus, 2005).

The CDAI is a validated composite index that was developed to simplify disease activity assessment in RA (Aletaha and Smolen, 2005) and consists of 28 Joint Count, Patient Global Assessment of Disease Activity, and Physician Global Assessment of Disease Activity.

The FACIT-F is validated to questionnaire used to assess fatigue in RA (Cella et al, 2005).

The HAQ-DI is a validated 20 item questionnaire to assess functional activity in specific tasks (Bruce and Fries, 2003).

Below are general instructions for the administration of these assessments. Specific instructions and questionnaires will be provided a separate document.

17.1 28 Joint Count

The 28 Joint Count includes assessment of swelling and tenderness in the shoulders, elbows, wrists, metacarpophalangeal joints, proximal interphalangeal joints and knees. The 28 Joint Count will be completed by the investigator or designee. The same rater should assess the subject at every visit.

17.2 Subject Completed Efficacy Questionnaires

The General Health VAS, Patient Assessment of Pain, Patient Global Assessment of Disease Activity, Patient Assessment of Physical Function by HAQ-DI, and FACIT-F are questionnaires to be completed by subjects. When these assessments are required, they should be the first assessments done at any visit and must be completed prior to any study drug dosing. Subjects will be provided a quiet, private place to complete the assessments. Subjects will be instructed to answer all questions to the best of their ability and without help from others (including study staff, relatives, or friends). The study staff should review the questionnaires after they are completed and encourage the subjects to complete any missing information. Subjects may refrain from answering any question. Study staff will record the refusal of subjects to answer any questions in the source documents.

17.3 Physician Completed Efficacy Questionnaires

The Physician Global Assessment of Disease Activity is a questionnaire to be completed by the investigator or designee. When this assessment is required, it should be the first assessment done at any visit and must be completed prior to any study drug dosing.

17.4 ESR and CRP

Blood samples for evaluation of ESR and CRP will be collected at times specified in the Schedule of Study Events (Table 7-1). Samples for ESR will be analyzed at the site. CRP samples will be shipped to a central laboratory.

Specific instructions for collection, processing, storage, and shipment of samples for ESR and CRP will be provided in a separate laboratory manual.

[REDACTED]

[REDACTED]

[REDACTED]

[REDACTED]

[REDACTED]

[REDACTED]

[REDACTED]

[REDACTED]

[REDACTED]

20.2 Analysis Populations

- The Modified Intent to Treat (mITT) Population will include all enrolled subjects who receive 1 or more doses of study drug and who contribute any efficacy data to the study.
- The Per-Protocol Population will include the subset of the mITT population who complete the study as per protocol.
- The Safety Population will include all enrolled subjects who receive 1 or more doses of study drug.

20.3 Endpoints

20.3.1 Primary Efficacy Endpoint

The primary efficacy endpoint will be the proportion of subjects with DAS28-ESR < 3.2 at Week 12.

20.3.2 Secondary Efficacy Endpoints

- Proportion of subjects who maintained DAS28-ESR < 3.2 from Week 12 through Week 24.
- Time to disease activity flare from Week 12 through Week 24.
- Proportion of subjects with CDAI \leq 10 at Week 12.
- Proportion of subjects who meet criteria for ACR20 at Week 12.

20.3.3 Secondary Safety Endpoints

- Summary of general safety profile, including adverse events (serious and non-serious), vital signs and laboratory assessments by study period and over the entire study.

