11 STUDY DESIGN

11.1 Description

This is a multicenter, multiple dose study to examine the effect of Acthar in adult subjects with RA with persistently active disease. Approximately 232 subjects will be enrolled.

During the first part of the study (Part 1-Open Label Period) all enrolled subjects will be treated with Acthar 1 mL (80 U) SC 2x/week for 12 weeks to assess the proportion of subjects who achieve LDA.

After 12 weeks of Acthar treatment, subjects who have achieved LDA (defined as DAS28-ESR < 3.2) will enter a double-blind randomized maintenance period (Part 2-Randomized Maintenance Period) and will be randomized in a 1:1 ratio into 2 groups:

- Group 1: Acthar 1 mL (80 U) SC 2x/week for an additional 12 weeks.
- Group 2: Placebo 1 mL SC 2x/week for an additional 12 weeks.

Subjects who do not achieve LDA at Week 12 will be discontinued from the study.

Subjects who experience a flare in disease activity will be discontinued from the study. Flare or worsening of disease activity is defined as:

- **Weeks 0 to 11:** DAS28-ESR ≥ 3.2 and increase of > 0.6 from the Week 0 assessment sustained over 2 consecutive study visits; **or** DAS28-ESR ≥ 3.2 and increased of > 1 from the Week 0 assessment at a single visit.
- **Weeks 13 to 23:** DAS28-ESR < 3.2 and increase of 1.2 from the Week 12 assessment; **or** DAS28-ESR ≥ 3.2 and increased of > 0.6 from the Week 12 assessment sustained over 2 consecutive study visits; **or** DAS28-ESR ≥ 3.2 and increase of > 1 from the Week 12 assessment at a single visit ([van der Maas, 2013](#)).

All subjects will have a Follow-up Visit 28 (± 2) days after their last dose of study drug.

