14.2 Baseline Visit (Week 0) and First Dose Procedures/Assessments

Predose evaluations will occur prior to the first dose of study drug.

The investigator or designee will complete the following procedures predose:

- Inclusion/exclusion criteria review; subject must meet all eligibility criteria at screening and baseline.
- Efficacy Questionnaires: General Health (VAS), Patient Assessment of Pain (VAS), Patient Global Assessment of Disease Activity (VAS), Patient Assessment of Physical Function assessed using the Health Assessment Questionnaire- Disability Index [HAQ-DI]), Functional Assessment of Chronic Illness Therapy- Fatigue Scale (FACIT-F) and Physician Global Assessment of Disease Activity (VAS).
- Work Productivity and Activities Impairment (WPAI).
- Current medical condition review.
- Limited physical examination.
- 28 Joint Count.
- Weight.
- Vital signs.
- Clinical laboratory tests.
- ESR and CRP.
- Urine pregnancy test.
- Vectra Disease Activity (Vectra[®] DA) sample.

- Serum and urine samples for [REDACTED]
[REDACTED]
[REDACTED]
[REDACTED] and urine creatinine.
- Subject diary training.
- Contact IXRS and confirm disease activity eligibility.
- Dispense study drug kits.
- Study drug administration under supervision of study staff and observation for at least 1 hour thereafter. Administration of all other doses will be done at home by the subject/caregiver.
- Adverse events and concomitant medications.

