20.3.6.1 Adverse Events

Adverse events will be coded using the appropriate version of MedDRA. All AEs will be presented in a data listing. Only treatment-emergent adverse events (TEAEs) (events that are new in onset or aggravated in severity following treatment) will be included in all summaries. TEAEs will be summarized for each treatment group, by system organ class and preferred term. Serious adverse events (including death) will be summarized. In addition, adverse events will be summarized by severity and relation to study drug.

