20.3.6.2 Clinical Laboratory Tests

Hematology, blood chemistry, urinalysis and HbA1c results will be summarized at baseline and at each visit by treatment group. Change from baseline to each visit will also be summarized. Abnormal laboratory values will be identified and analyzed.

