20.3.6.3 Vital Signs

Vital sign results (heart rate, diastolic/systolic blood pressures, respiratory rate, and body temperature) and corresponding changes from baseline values will be summarized at each visit with descriptive statistics by treatment group.

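### The Part 2 safety comparison has no adjustment for time at risk and no change from Week 12, and the entire-study tables have no stated column rule

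*Combined protocol and SAP*

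**What the plan says.** Section 20.3.3 sets the frame for safety reporting: "vital signs and laboratory assessments by study period and over the entire study". A Part 2 summary is therefore planned beside an entire-study one.

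Section 20.3.6 gives the layout:

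- **Adverse events (20.3.6.1).** "TEAEs will be summarized for each treatment group, by system organ class and preferred term". Treatment-emergent means "events that are new in onset or aggravated in severity following treatment". No rate per subject-time is mentioned, no rule assigns an event to the treatment at onset, and emergence does not restart at randomisation.
- **Laboratory (20.3.6.2).** "Hematology, blood chemistry, urinalysis and HbA1c results will be summarized at baseline and at each visit by treatment group", and then "Change from baseline to each visit will also be summarized".
- **Vital signs (20.3.6.3).** Results and "corresponding changes from baseline values will be summarized at each visit with descriptive statistics by treatment group".

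The only visit labelled baseline is Week 0: Table 7-1 and the title of Section 14.2, "Baseline Visit (Week 0) and First Dose Procedures/Assessments". Section 11.1 says of Part 1 that "all enrolled subjects will be treated with Acthar 1 mL (80 U) SC 2x/week for 12 weeks". Subjects with low disease activity (LDA) at Week 12 are then randomised 1:1 to Acthar or placebo for 12 more weeks, and the rest leave. The Safety Population in Section 20.2 is everyone dosed; no separate Part 2 safety set is defined.

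**The concern.** Safety and tolerability is a secondary objective (Section 10.2), and Part 2 is the only concurrent placebo control in the trial. Three features make that control less informative than the data allow.

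(a) A subject who flares leaves the study (Sections 11.1, 15.3.1 and 22.1), and the plan expects placebo to hold LDA less often. Incidences without a time denominator would then compare a longer-observed Acthar group with a shorter-observed placebo group, making Acthar look relatively worse.

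(b) A Part 2 change measured from Week 0 combines the Part 1 Acthar effect with whatever follows randomisation. In the placebo column these can pull in opposite directions, so that column's change is neither a placebo effect nor a withdrawal effect.

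(c) The entire-study tables need columns, and the visible text does not say which. Under randomised-group columns, Part 1 Acthar events of placebo subjects would count under placebo, pulling the contrast towards no difference. Subjects never randomised would have no column.

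**Working it through.** **The plan's own figures (Section 20.7).** With 52 per group, 80% v 50% and 2-sided 0.05, the pooled proportion is 0.65. The null standard error is √(2×0.65×0.35/52) = 0.0935 and the alternative one is √((0.16+0.25)/52) = 0.0888. Then z = (0.30 − 1.96×0.0935)/0.0888 = 1.31, giving power 0.906; the stated 90% reproduces. Also 0.45×232 = 104.4 randomised and 0.55×232 = 127.6, about 128, never randomised. These are efficacy figures; none is stated for safety.

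**(a) Time at risk.** Inputs: 80% and 50% keeping LDA over 12 weeks. Assume every loss is a withdrawal at a constant rate. With S the proportion remaining at 12 weeks, mean time on study is 12(1−S)/(−ln S).

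- Acthar: 12×0.20/0.2231 = 10.8 weeks.
- Placebo: 12×0.50/0.6931 = 8.7 weeks, about 20% less.

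If only half the losses lead to withdrawal (S = 0.90 v 0.75), the means are 12×0.10/0.1054 = 11.4 and 12×0.25/0.2877 = 10.4 weeks, about 8% less.

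Effect on a crude percentage: suppose the event hazard is the same in both groups, equal to 20% per 12 weeks (assumed), so h = 0.2231 per 12 weeks. With withdrawal hazard w, the proportion with an event before withdrawal or Week 24 is h/(h+w) × (1−e^−(h+w)).

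- Acthar (w = 0.2231): 0.500×(1−0.64) = 18.0%.
- Placebo (w = 0.6931): 0.2435×(1−0.40) = 14.6%.

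Equal hazards thus show a gap of 3.4 points under full withdrawal.

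**(b) Week 0 or Week 12.** Change from Week 0 to Week 24 is (Week 12 − Week 0) + (Week 24 − Week 12). Both groups had the same Part 1 treatment and were then randomised, so the first bracket has equal expectation in each and cancels in the between-arm difference. What remains is readability and possibly precision. With equal SDs at each visit, the SD of change from Week 12 relative to change from Week 0 is √[(1−r₁₂,₂₄)/(1−r₀,₂₄)]. At assumed correlations of 0.7 and 0.5 this is √(0.3/0.5) = 0.775, or 23% smaller; at equal correlations it is 1, with no gain. The documents give no correlations.

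**(c) Entire-study columns.** Let q be the Part 1 incidence and p the Part 2 incidence, assumed independent. If columns are the randomised groups, entire-study incidence is 1−(1−q)(1−p), and the Part 2 gap is multiplied by (1−q). All rates below are assumed; the documents give none.

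| Part 1 | Part 2, Acthar v placebo | Entire study | Gap (points) | Risk ratio |
|---|---|---|---|---|
| 10% | 10% v 5% | 19.0% v 14.5% | 5.0 → 4.5 | 2.00 → 1.31 |
| 20% | 20% v 10% | 36.0% v 28.0% | 10 → 8 | 2.00 → 1.29 |
| 40% | 40% v 20% | 64.0% v 52.0% | 20 → 12 | 2.00 → 1.23 |
| 5% | 20% v 10% | 24.0% v 14.5% | 10 → 9.5 | 2.00 → 1.66 |
| 40% | 20% v 10% | 52.0% v 46.0% | 10 → 6 | 2.00 → 1.13 |

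A Part 2-only table is not diluted in this way.

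**The case against.** The best defence is that the plan already contains the table that matters. Reporting by study period, read with Section 20.3.6, gives a Part 2 summary by treatment group. That stands, and it rules out a reading that a reader might reach from the entire-study wording alone: that the randomised safety contrast is lost.

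Two other stronger readings also fail.

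- A reader might infer that the plan charges Part 1 Acthar events to placebo. No visible text says so. Groups 1 and 2 exist only from Week 12, disposition is split between Part 1 enrolled and Part 2 randomised subjects (Section 20.3.5.4), and columns by treatment at onset fit the wording equally well. The column rule is undefined, which is not the same as wrong.
- A reader might infer that return of laboratory values or blood pressure after the switch to placebo cannot be seen. Values are tabulated at each visit by group, and Table 7-1 schedules chemistry, haematology, urinalysis and vital signs at Weeks 12, 16, 20 and 24, and HbA1c at Weeks 12 and 24. The movement can be read from group means, although subjects who leave change the denominators from row to row.

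It is also fair to say that Section 20.1 is not visible and may define baseline or treatment group; that safety summaries are descriptive, with no test whose power suffers; and that losing LDA is not the same as meeting the flare definition, so the 20% difference in observation time overstates the share of losses that become withdrawals. Equal Part 1 and Part 2 Acthar rates are doubtful too, because those randomised are Week 12 responders who stayed on treatment.

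None of this supplies a time denominator in Section 20.3.6.1 or a change from the point of randomisation in Sections 20.3.6.2 and 20.3.6.3.

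**Conclusion.** The point holds as a minor to moderate weakness in how safety is tabulated. The Part 2 summary preserves the randomised contrast, and the Week 0 reference does not bias the between-arm difference.

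- **Time at risk** is the most concrete gap, because it affects the Part 2 table itself. Mean time would be about 8% to 20% shorter on placebo if half to all of the expected losses of LDA became constant-rate withdrawals.
- **Change from Week 0** makes the placebo column hard to interpret. A precision gain from Week 12 is plausible but rests on unknown correlations, from none to about 23% in the cases shown.
- **Entire-study columns** are conditional: only if they follow randomised group does the gap shrink by the factor (1−q), which is slight for uncommon events and substantial for common ones.

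The LDA rates are the plan's own; the event rates, correlations, independence and withdrawal pattern are assumptions. Efficacy, alpha and sample size are unaffected.

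**What to change.** In Section 20.3.6:

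1. Name the Part 2 summary in randomised subjects as the Acthar v placebo safety comparison, and add event rates per subject-time to the incidences.
2. For Part 2 laboratory values and vital signs, report change from Week 12 as well as from Week 0. State the baseline for each parameter: HbA1c is not scheduled at Week 0 in Table 7-1, so its pre-treatment value is the Screening one.
3. In entire-study tables, assign each event to the treatment at onset, and count subjects never randomised under Part 1 Acthar exposure.

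Onset dates and Week 12 measurements are already collected, so the cost is table shells, programming and a few more tables. Two limits should be noted in the text: rates per subject-time do not remove selection caused by flare withdrawal, and treatment at onset cannot separate a late Acthar effect from an event arising on placebo early in Part 2.

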20.3.4 Exploratory Endpoints

Exploratory Efficacy Endpoints

- [REDACTED]
- [REDACTED]
- [REDACTED]
- [REDACTED]
- [REDACTED]

- [REDACTED]

Exploratory Health Outcomes Related Endpoints

- [REDACTED]
- [REDACTED]
- [REDACTED]
- [REDACTED]
- [REDACTED]

Exploratory [REDACTED]

- [REDACTED]
- [REDACTED]
- [REDACTED]
- [REDACTED]
- [REDACTED]

20.3.5 Subject Characteristics

20.3.5.1 Demographics

The demographic information will be summarized for each analysis population by treatment group.

20.3.5.2 Medical and Surgical History

Relevant prior medical conditions or procedures will be summarized by body system and treatment group.

20.3.5.3 Prior and Concomitant Medications

Prior and concomitant medications will be coded according to the WHO Drug Dictionary. The incidence (number and percent) of prior and concomitant medication use will be summarized by treatment group.

20.3.5.4 Subject Disposition and Exposure to Study Drug

Subject disposition will be summarized for all enrolled subjects in Part 1 and all randomized subjects in Part 2. The number of subjects who complete the study and who do not complete the study along with the reasons for discontinuation from the study will be summarized.

20.3.6 Safety Analysis

All subjects who receive at least 1 dose of study drug will be included in the safety analyses. Safety data will be summarized descriptively or graphically, as appropriate.

20.3.6.1 Adverse Events

Adverse events will be coded using the appropriate version of MedDRA. All AEs will be presented in a data listing. Only treatment-emergent adverse events (TEAEs) (events that are new in onset or aggravated in severity following treatment) will be included in all summaries. TEAEs will be summarized for each treatment group, by system organ class and preferred term. Serious adverse events (including death) will be summarized. In addition, adverse events will be summarized by severity and relation to study drug.

20.3.6.2 Clinical Laboratory Tests

Hematology, blood chemistry, urinalysis and HbA1c results will be summarized at baseline and at each visit by treatment group. Change from baseline to each visit will also be summarized. Abnormal laboratory values will be identified and analyzed.

20.3.6.3 Vital Signs

Vital sign results (heart rate, diastolic/systolic blood pressures, respiratory rate, and body temperature) and corresponding changes from baseline values will be summarized at each visit with descriptive statistics by treatment group.

20.3.6.4 Other Safety Analysis

Other safety assessments including physical examinations, weight, and pregnancy testing, will be analyzed with appropriate summary statistics.

20.3.7 Efficacy Analysis

All efficacy analyses will be performed on the mITT. Selected analyses will be performed on the Per-protocol Population.

20.6 Interim Analysis

The study results from Part 1 will be summarized when all subjects complete the Part 1 of the study. No other interim analyses are planned for this study.

20.7 Statistical Power and Sample Size Considerations

It is expected that 360 subjects will be screened and a total of 232 subjects will be enrolled in this study. It is estimated that 55% of subjects will either drop out before Week 12 or will not achieve LDA by Week 12. The remaining 45% of subjects will have achieved LDA after 12 weeks of treatment with Acthar and will be randomized into 2 treatment groups in Part 2 of the study. Based on results from previous studies ([Pincus, 2011](#)) and ([Ruperto et al, 2008](#)), it is estimated that 80% of the Acthar group and 50% of the placebo group will maintain LDA after the 12 additional weeks of treatment. Assuming that 52 subjects per group (104 subjects total) will complete Part 2, and based on the use of a 2-sided, 2-sample comparison of proportions at the $\alpha = 0.05$ level of significance, there will be 90% of power to detect a difference in the 2 treatment groups.

20.8 Deviations From Statistical Analysis Plan

Any deviations from the planned statistical analysis will be described and justified in the final clinical study report as appropriate.

21 ADVERSE EVENTS AND SERIOUS ADVERSE EVENTS

21.1 Safety

For safety information about Acthar refer to the most recent version of the Prescribing Information ([Mallinckrodt ARD, 2015](#)) and the Investigator's Brochure ([Mallinckrodt, 2016](#)).

21.2 Definitions

Adverse Event

An AE is any untoward or undesirable medical occurrence in a subject who is administered IMP, which does not necessarily have to have a causal relationship with this treatment.

Examples of AEs include but are not limited to:

- Clinically significant laboratory findings.
- Clinically significant changes in physical examination findings.
- An AE occurring due to IMP overdose whether accidental or intentional.

- An AE occurring from IMP abuse.
- An AE associated with IMP withdrawal.
- Unexpected Adverse Event.

An unexpected AE is defined as an AE, the nature and severity of which is not consistent with the applicable product information in the most recent version of the Investigator's Brochure.

Serious Adverse Event

An SAE is defined as any untoward medical occurrence that at any dose results in any of the following outcomes:

- Death.
- A life-threatening AE.
- Inpatient hospitalization or prolongation of existing hospitalization.
- A persistent or significant incapacity or substantial disruption of the ability to conduct normal life functions.
- Results in a congenital anomaly/birth defect.

Important medical events that may not result in death, be life-threatening, or require hospitalization may be considered serious when, based upon appropriate medical judgment, may jeopardize the subject or subject and may require medical or surgical intervention to prevent one of the outcomes listed above. Examples of such medical events include allergic bronchospasm requiring intensive treatment in an emergency department or at home, blood dyscrasias or convulsions that do not result in inpatient hospitalization, or the development of drug dependency or drug abuse.

Death

Death is an outcome of an event. The event that resulted in death should be recorded and reported on the SAE Form. All causes of death must be reported as SAEs. The investigator should make every effort to obtain and send death certificates and autopsy reports to Mallinckrodt.

Life-Threatening Event

A life-threatening event refers to immediate risk of death as the event occurred per the reporter. A life-threatening event does not include an event that, had it occurred in a more

severe form, might have caused death but, as it actually occurred, did not create an immediate risk of death. For example, hepatitis that resolved without evidence of hepatic failure would not be considered life-threatening, even though hepatitis of a more severe nature can be fatal. Similarly, an allergic reaction resulting in angioedema of the face would not be life-threatening, even though angioedema of the larynx, allergic bronchospasm, or anaphylaxis can be fatal.

Hospitalization

Hospitalization is defined as an official admission to a hospital. Hospitalization or prolongation of a hospitalization constitutes a criterion for an AE to be serious; however, it is not in itself considered an SAE. In absence of an AE, a hospitalization or prolongation of a hospitalization should not be reported by the investigator as an SAE. Such situations include, but are not limited to, the following:

A hospitalization or prolongation of hospitalization is needed for a procedure required by the protocol.

A hospitalization or prolongation of hospitalization is part of a routine procedure followed by the center (eg, stent removal after surgery). This should be recorded in the study file.

A hospitalization for a preexisting condition that has not worsened.

Note that the following hospitalizations are not considered SAEs in Mallinckrodt clinical studies:

A visit to the emergency department or other hospital department of less than 24 hours that does not result in admission (unless considered "important medical event" or life-threatening event).

